### **10.1 Analysis sets**

#### **10.1.1 Full Analysis Set**

The Full Analysis Set (FAS) comprises all patients to whom study treatment has been assigned by randomization. According to the intent to treat principle, patients will be analyzed according to the treatment (and strata) they have been assigned to during the randomization procedure. The FAS will be the primary population for all efficacy related data analyses.

#### **10.1.2 Safety Set**

The Safety Set includes all patients who received at least one dose of study medication and have at least one valid post-screening/post-baseline safety assessment. Patients will be analyzed according to the study treatment (regimen) they actually received. The statement that a patient had no AEs (on the AE eCRF) constitutes a valid safety assessment. Patients will be classified according to treatment received, where treatment received is defined as:

- The treatment assigned if it was received at least once, or
- If the assigned treatment was never received, then the first treatment received when starting therapy with study treatment will be used for classification

The safety set will be the primary population for all safety related endpoints.

A precise definition of “actually received” will be added in the Reporting and Analysis Plan (RAP).

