3. Its relationship to the study treatment (Reasonable possibility that AE is related: No, Yes)
4. Action taken with respect to study or investigational treatment (none, dose adjusted, temporarily interrupted, permanently discontinued, unknown, not applicable)
5. Whether medication or therapy was given (no concomitant medication/non-drug therapy, concomitant medication/non-drug therapy)

6. Outcome (not recovered/not resolved, recovered/resolved, recovering/resolving, recovered/resolved with sequelae, fatal, unknown)
7. Whether it is serious, where a serious adverse event (SAE) is defined as in [Section 8.2.1](#). and which seriousness criteria have been met.

All adverse events should be treated appropriately. If a concomitant medication or non-drug therapy is given, this action should be recorded on the Adverse Event eCRF.

Once an adverse event is detected, it should be followed until its resolution or until it is judged to be permanent, and assessment should be made at each visit (or more frequently, if necessary) of any changes in severity, the suspected relationship to the study treatment, the interventions required to treat it, and the outcome.

Progression of malignancy (including fatal outcomes), if documented by use of appropriate method (for example, as per irRC or as per RECIST), should not be reported as a serious adverse event.

Adverse events separate from the progression of malignancy (example, deep vein thrombosis at the time of progression or hemoptysis concurrent with finding of disease progression) will be reported as per usual guidelines used for such events with proper attribution regarding relatedness to the drug.

After initiation of new post-treatment antineoplastic therapy, only AEs suspected to be related to study treatment will be collected in the Adverse Events CRF.

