2.2 Analysis sets

The number (%) of patients in each of the defined analysis set will be summarized using the FAS.

Full Analysis Set

The Full Analysis Set (FAS) comprises all patients to whom study treatment has been assigned by randomization. According to the intent to treat principle, patients will be analyzed according to the treatment (and strata) they have been assigned to during the randomization procedure. The FAS will be the primary population for all efficacy related data analyses.

Safety Set

The Safety Set includes all patients who received at least one dose of study medication and have at least one valid post-screening/post-baseline safety assessment. Patients will be analyzed according to the study treatment (regimen) they received.

The statement that a patient had no AEs (on the AE eCRF) constitutes a valid safety assessment. Patients will be classified according to treatment received, where treatment received is defined as:

- The treatment assigned if it was received at least once, or
- If the assigned treatment was never received, then the first treatment received when starting therapy with study treatment will be used for classification

The safety set will be the primary population for all safety related endpoints.

Per-protocol Set

The Per Protocol Set (PPS) consists of a subset of FAS patients who meet the following criteria:

- Treatment according to the randomization scheme (see [CPDR01X2201-Protocol-Section 6](#)).
- Presence of at least one measurable lesion at screening/baseline according to RECIST v1.1 as per [CPDR01X2201-Protocol-Appendix 1](#).
- At least 2 post-screening/post-baseline tumor assessments (unless disease progression is observed before that time).
- Have not been previously treated with PD-1- or PD-L1-directed therapy or any therapeutic cancer vaccine.

Patients will be classified according to treatment received.

In the final CRS no sensitivity analysis with PPS will be conducted.

Pharmacokinetic analysis set

The pharmacokinetic analysis set (PAS) consists of all patients who have at least one dose of PDR001 and have at least one evaluable concentration measurement of PDR001. The PAS will be used for all PK analyses.

Note: Patients may be removed from the estimation of certain PK parameters on an individual basis depending on the number of available blood samples. These patients will be identified at the time of analysis along with their reason for removal.

Immunogenicity (IG) analysis set

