2.2.1 Analysis set exclusion

Patients will be excluded from the analysis sets based on the protocol deviations and specific non-protocol deviations entered in the database. All protocol deviations and non-protocol

deviations leading to exclusion from specific analysis sets will be identified before database lock. Details in Table 2-1.

Table 2-1 Protocol deviation and non-protocol deviation leading to exclusion from analysis set definitions

Analysis set	PDs leading to exclusion (ID)	Non-PDs leading to exclusion
FAS Safety set	No written inform consent (INCL01).	No administration of study drug. No valid post-baseline safety assessment.
PPS	No written inform consent (INCL01). Receive study treatment not according to the randomization scheme (i.e., randomize to PDR but receive Chemotherapy, vice versa) (TRT01, TRT02) Patient has no measurable lesion as determined by RECIST 1.1 at baseline (INCL09) Have been previously treated with PD-1- or PD-L1-directed therapy or any therapeutic cancer vaccine. (INCL14)	No administration of study drug. Less than 2 post-screening/post-baseline tumor assessments (unless disease progression is observed before that time).
PAS	No written inform consent (INCL01).	No administration of study drug. No evaluable PK data.
Immunogenicity prevalence set	No written inform consent (INCL01).	No administration of study drug. No determinant IG sample at both baseline and post-baseline
Immunogenicity incidence set	No written inform consent (INCL01).	No administration of study drug No determinant IG sample at baseline or post-baseline or both

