2.8 Safety analysis

Summaries and listings described in this section will be done by study treatment groups based on the Safety set:

- PDR001
- Chemotherapy
- Crossover

For crossover treatment group, summaries will be done if there are more than 10 crossover patients.

The assessment of safety is based on the type and frequency of Adverse Events (AEs) as well as on the number of laboratory values that fall outside of pre-determined ranges (Common Toxicity Criteria for Adverse Events (CTCAE) grading limits or normal ranges as appropriate). Other safety data include electrocardiogram and vital signs.

The overall observation period will be divided into three mutually exclusive segments:

- Pre-treatment period: from day of patient's informed consent to the day before first dose of study treatment,
- On-treatment period: from day of first dose of study treatment to the end of safety follow up, i.e., for PDR001, to 30 days after last dose of PDR001; For chemotherapy, to 30 days after last dose of chemotherapy.

- Post-treatment period: starting at Day 31 after last dose of PDR001 for PDR001 treatment group; Starting at Day 31 after last dose of chemotherapy for chemotherapy treatment group.

If dates are incomplete in a way that clear assignment to pre-, on-, post-treatment period cannot be made, then the respective data will be assigned to the on-treatment period.

Safety summaries will primarily be based on all data from the on-treatment period. Following last administration of PDR001, adverse events (including serious adverse events), and new antineoplastic therapies are collected for a period of 150 days. Following start of new antineoplastic therapy only treatment related adverse events will be collected. Select summaries of related adverse events will be produced for the combined on-treatment and post-treatment periods ([Section 2.8.1](#)).

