- AEs suspected to be study treatment related;
- SAEs related to study treatment

The following listings will be produced:

- All adverse events (safety set)

Deaths (CSR Outputs)

Separate summaries for on-treatment and all deaths (including post-treatment deaths) will be produced by treatment arm, system organ class and preferred term.

All deaths will be listed for the safety set, deaths occurring after the treatment period will be flagged.

EudraCT and clinicaltrials.gov requirements for AEs and Deaths summaries

For the legal requirements of clinicaltrials.gov and EudraCT, two required tables on treatment-emergent adverse events which are not serious adverse events with an incidence greater than 5% and on treatment emergent SAEs and SAEs suspected to be related to study treatment will be provided by SOC and PT on the safety set population. These summaries will include any events starting or worsening in the on-treatment period.

If for a same patient, several consecutive AEs (irrespective of study treatment causality, seriousness and severity) occurred with the same SOC and PT:

- a single occurrence will be counted if there is ≤ 1 day gap between the end date of the preceding AE and the start date of the consecutive AE
- more than one occurrence will be counted if there is > 1 day gap between the end date of the preceding AE and the start date of the consecutive AE

For occurrence, the presence of at least one SAE / SAE suspected to be related to study treatment / non SAE has to be checked in a block e.g., among AE's in a ≤ 1 day gap block, if at least one SAE is occurring, then one occurrence is calculated for that SAE.

The number of deaths resulting from SAEs suspected to be related to study treatment and SAEs irrespective of study treatment relationship will be provided by PT.

Adverse events of special interests / grouping of AEs

An adverse event of special interest is a grouping of adverse events that are of scientific and medical concern specific to compound PDR001. These groupings are defined using MedDRA terms, SMQs (standardized MedDRA queries), HGLTs (high level group terms), HLT (high

[figure not shown]

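### The Safety Set requires a post-baseline safety assessment as well as a dose, which leaves a narrow gap: a treated patient who dies or is lost very early with no safety record would be missing from the safety death tables and listing

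*Protocol*

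**What the plan says.** Protocol 10.1.2 sets two conditions for the Safety Set, a dose and a later assessment: "received at least one dose of study medication and have at least one valid post-screening/post-baseline safety assessment". It then widens the second condition: "The statement that a patient had no AEs (on the AE eCRF) constitutes a valid safety assessment". It also gives the set its role: "The safety set will be the primary population for all safety related endpoints".

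SAP 2.2 repeats the rule ("The Safety Set includes all patients who received at least one dose of study medication and have at least one valid post-screening/post-baseline safety assessment") and the allowance for an entry of no AEs. SAP Table 2-1 makes it operational by listing "No valid post-baseline safety assessment" as a reason for exclusion.

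The set governs the safety reporting. SAP 2.8 opens with "Summaries and listings described in this section will be done by study treatment groups based on the Safety set", and SAP 2.8.1 says of deaths: "All deaths will be listed for the safety set". The on-treatment and all-death summaries in that section use the same population.

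Deaths are collected on a separate Death form, and CTCAE grade 5 is not used (protocol 8.1.1). The same section says that "Progression of malignancy (including fatal outcomes), if documented by use of appropriate method" is not to be reported as a serious adverse event.

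**The concern.** A safety population is normally fixed by exposure alone. Here a patient who has been dosed can still drop out of it because of what did or did not get recorded afterwards. The patients least likely to have a later assessment are those who die or disappear almost at once.

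The route for a death is specific. A death from documented progression need not produce an SAE, and under protocol 8.2.1 progression that clearly fits the cancer is not reported as an AE. Such a death could exist only on the Death form, and neither document says whether a Death-form entry is a valid safety assessment. If it is not, the patient leaves the tables that show on-treatment deaths by system organ class and preferred term, and leaves the death listing. Eligibility admits pretreated recurrent or metastatic disease with ECOG status up to 2 (protocol 5.2), so an early death is plausible.

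**Working it through.** The plan gives no figure on this point, so the check is a reading of the rules followed by an illustration of size.

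**1. Who is excluded.** Under protocol 10.1.2, SAP 2.2 and SAP Table 2-1, a treated patient is excluded only if all of the following hold:
- no AE entry;
- no statement on the AE page that there were none;
- no post-dose laboratory value, vital sign, ECG or examination (the safety measures named in protocol 7.2.2).

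Early death or loss alone is not enough.

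**2. What the excluded patient is missing from.** The SAP 2.8.1 death summaries and death listing, and the AE tables and listing.

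**3. What still captures the patient.**
- SAP 2.7 and Table 2-3: the number and percentage of deaths are summarised in the overall survival analysis on the Full Analysis Set, and OS is listed by patient.
- SAP 2.3.1: disposition, with reasons for discontinuation, is on the Full Analysis Set.
- SAP 2.2: the size of each analysis set is tabulated against the Full Analysis Set, so an exclusion shows as a count.

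**4. Which arm is more exposed.**
- PDR001: protocol Table 7-7 schedules an ECG 1 hour after the first dose, and Table 7-1 has vital signs, hematology and chemistry on Day 15. The ECG plan ended with Amendment 05 (30 Aug 2018), after the last patient's first dose (3 Aug 2018).
- Chemotherapy: the legible part of the visit schedule (Table 7-2) shows visits only on Day 1 of each cycle, and an ECG only at screening.
- The gap is therefore probably wider in the chemotherapy arm.

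**5. Size, by illustration.** Inputs: 122 randomised, 82 to PDR001 (protocol, Amendment 06 study status), so 122 − 82 = 40 to chemotherapy. Assumptions: all randomised patients were treated, each excluded patient is an early death, and there are no other deaths. With k excluded deaths among n patients, the proportion is k/n on an all-treated set and 0/(n − k) on the Safety Set. Exact (Clopper-Pearson) 95% limits are shown for k = 1.

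| Arm | k | All treated | Safety Set as written |
|---|---|---|---|
| PDR001 | 1 | 1/82 = 1.2% (0.0 to 6.6) | 0/81 = 0% (0 to 4.5) |
| PDR001 | 3 | 3/82 = 3.7% | 0/79 = 0% |
| Chemotherapy | 1 | 1/40 = 2.5% (0.1 to 13.2) | 0/39 = 0% (0 to 9.0) |
| Chemotherapy | 3 | 3/40 = 7.5% | 0/37 = 0% |

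The range k = 1 to 3 is assumed; the documents do not give the number. With k = 0 nothing changes.

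**6. Direction for AE percentages.** A patient with no AE record adds nothing to the numerator. Dropping one such patient multiplies an AE percentage by 82/81 = 1.012 on PDR001 or 40/39 = 1.026 on chemotherapy, so AE percentages rise slightly.

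**The case against.** The strongest reply is that the documents already close most of the gap.

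- The allowance for an entry of no AEs keeps in anyone whose AE page was completed. This stands, but someone has to complete the page, and that is least certain for a patient who died or vanished after one dose.
- Fatal progression escapes SAE reporting only if it is documented (protocol 8.1.1). The first scheduled scan is at 8 weeks (Table 7-4), and clinical suspicion of progression before then calls for a physical examination as well as imaging (protocol 7.2.1), which would itself leave a safety record. If progression is not documented, a fatal event is an SAE, and any doubt about cause is to be reported (protocol 8.2.1). This largely stands: either branch would normally create a record. The remainder depends on those steps being carried out and entered.
- Deaths are counted elsewhere. This stands for the total number of deaths. The OS summary is by randomised arm, though, and does not give on-treatment status or preferred term. The analysis-set table shows that someone was excluded, not that the person died.

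A reader might infer three stronger things. One is that early deaths vanish from the trial's reporting; the FAS-based OS analysis contradicts that. Another is that safety rates in general are understated; this can apply only to Safety Set death counts, since AE percentages move the other way. The third is that the rule chiefly hides rapid deterioration after a first PDR001 dose; the 1-hour ECG makes that arm the better protected one.

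**Conclusion.** The point holds as a minor flaw of definition. As written, a treated patient can be left out of the primary safety population for lack of a later record, and neither document says that a Death-form entry prevents this. The exposure is narrow, probably wider on chemotherapy, and limited to the Safety Set death summaries and death listing.

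One affected patient would be worth 1.2 percentage points on PDR001 or 2.5 on chemotherapy in the death proportion, under the assumptions in step 5. Those figures use randomised rather than treated numbers. How many patients are affected cannot be read from the documents. No figure in either document needs correcting.

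**What to change.** In protocol 10.1.2 and SAP 2.2, define the Safety Set as every patient given at least one dose of study treatment. In SAP Table 2-1, delete "No valid post-baseline safety assessment" as a Safety Set exclusion. Stating only that a Death-form entry counts as an assessment would rescue the deaths but still leave out patients lost after one dose, so the exposure-based definition is cleaner.

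The change removes one clause from each document and one table entry, needs no new data, and can only add treated patients. SAP Section 1 provides the route: an amendment before database lock or an addendum after it. The one downside is that, if any patient is affected, the final safety denominators would differ slightly from those in the interim CSR. A footnote giving the number of patients added, by arm, would explain that.

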#### **10.1.3 Per-Protocol Set**

The Per Protocol Set (PPS) consists of a subset of FAS patients who meet the following criteria:

- Treatment according to the randomization scheme (see [Section 6](#)).
- Presence of at least one measurable lesion at screening/baseline according to RECIST v1.1 as per [Appendix 1](#).
- At least 2 post-screening/post-baseline tumor assessments (unless disease progression is observed before that time).

- Have not been previously treated with PD-1- or PD-L1-directed therapy or any therapeutic cancer vaccine.

Patients will be classified according to treatment received.

The PPS will define the patients used in the sensitivity analysis of the primary endpoint (see [Section 10.4.4](#)). If the PPS and the FAS are identical, then analyses described by the PPS below will not be performed.

All protocol deviations leading to exclusion from the PPS will be detailed in the RAP.

#### **10.1.4 Pharmacokinetic analysis set**

The pharmacokinetic analysis set (PAS) consists of all patients who have at least one dose of PDR001 and have at least one evaluable concentration measurement of PDR001. The PAS will be used for all PK analyses.

Note: Patients may be removed from the estimation of certain PK parameters on an individual basis depending on the number of available blood samples. These patients will be identified at the time of analysis along with their reason for removal.

#### **10.2 Patient demographics/other screening/baseline characteristics**

Demographic and other screening/baseline data including age, gender, height, weight, medical condition, and disease characteristics will be summarized descriptively by treatment arm on the FAS.

#### **10.3 Treatments (study treatment, concomitant therapies, compliance)**

##### **10.3.1 Study treatment**

The actual dose and duration in days of PDR001 and as well as the dose intensity (computed as the ratio of actual dose received and actual duration) and the relative dose intensity (computed as the ratio of dose intensity and planned dose received/planned duration), will be listed and summarized by means of descriptive statistics. Categories for relative dose intensity of PDR001 will be specified as  $< 0.5$ ,  $\geq 0.5 - < 0.75$ ,  $\geq 0.75 - < 0.9$ ,  $\geq 0.9 - < 1.1$  and  $\geq 1.1$ . The number and proportion of patients falling in each category will be presented. The summary data will be presented for each treatment cycle individually, as well as for all study days as a single category using descriptive statistics (e.g. mean, median, and modal doses). Similar analysis will be performed for the patients included in the control arm.

##### **10.3.2 Concomitant therapies**

Concomitant medications and significant non-drug therapies prior to and after the start of the study drug treatment will be listed by patient and summarized by ATC (anatomical therapeutic chemical classification system) term.

### 10.3.3 Compliance

Compliance to the protocol will be assessed by the number and proportion of patients with protocol deviations. These will be identified prior to database lock and will be listed and summarized by treatment group/study arm. Compliance to the study drug will be assessed by the number of dose reductions and dose interruptions, see [Section 10.5](#).

## 10.4 Primary objective

The primary objective of the Phase II study is to assess any improvement in the anti-tumor effects of the PDR001 versus investigator's choice of treatment in patients with moderately differentiated/undifferentiated locally advanced recurrent or metastatic NPC who progressed on or after first-line therapy.

### 10.4.1 Variable

The primary efficacy endpoint in this study is progression-free survival (PFS) based on central review of tumor scan, as defined per RECIST v1.1 ([Appendix 1](#)).

PFS is the time from the date of randomization to the date of event defined as the first documented confirmed progression or death due to any cause. If a patient has not had an event, progression-free survival is censored at the date of last adequate tumor assessment.

### 10.4.2 Statistical hypothesis, model, and method of analysis

Patients are randomized in 2:1 ratio into either PDR001 arm or control arm. The primary efficacy endpoint, PFS as determined based on the central tumor assessment per RECIST v1.1, will be analyzed by study arm. Assuming proportional hazards for PFS, the following statistical hypothesis will be tested to address the primary efficacy objective:

$$H_{01}: \theta_1 \geq 1 \text{ vs. } H_{A1}: \theta_1 < 1$$

where  $\theta_1$  is the PFS hazard ratio (PDR001 arm vs control arm). The analysis to test this hypothesis will consist of a stratified log-rank test at an overall one-sided 10% level of significance. The stratification factor is disease status (locally advanced recurrent NPC vs. metastatic NPC).

As a supportive analysis, a Bayesian Cox proportional hazard (PH) model (see [Appendix 3](#)) will be used to estimate the hazard ratio for PFS between the two treatment combination arms. The final analysis will be performed when 70 events (progressive disease or death due to any cause) are observed from the study.

An evidence-based prior for the non-parametric, interval-specific hazards of the control arm in the Bayesian Cox PH model is derived using available historical PFS data from the list of the phase II studies (see [Table 1-1](#) and [Appendix 3](#)), using the meta-analytic-predictive (MAP) approach ([Neuenschwander et al 2010](#)) with the assumption of moderate/large between-trial heterogeneity. For more details about the model specification including the prior derivation and its operating characteristics please refer to [Appendix 3](#).

Based on the historical studies, the median PFS for the patients in the control arm is assumed to be 5.5 months (165 days).

The dual-criterion for success based on Bayesian Cox PH model is defined to show a positive result if there is enough evidence that monotherapy PDR001 is superior to the control with respect to the primary PFS endpoint, such that:

- Posterior probability ( $HR > 1$ )  $< 10\%$ , and
- Posterior median  $HR < 0.7$

The posterior median of the HRs along with the associated 95% two-sided credible intervals will be produced for the treatment comparison of PDR001 to the control. In addition, the posterior probability that the true HR lies in the following intervals will be produced:

- Substantial efficacy:  $[0, 0.55)$
- Moderate efficacy:  $[0.55, 0.7)$
- Slight efficacy:  $[0.7, 1)$
- No efficacy:  $[1, \infty)$

Moreover, Kaplan-Meier plots will be provided in order to present PFS graphical outputs for the PDR001 and the control arm. KM estimates of the median and PFS rates at 2, 4, 6, 8, 10 and 12 months will be given along with 95% confidence intervals. The FAS will be used for the primary analysis. A stratified Cox regression model will also be used to estimate the HR of PFS as supplementary analysis,

